#### Covariance Structure Strategy

The unstructured covariance structure for the within-patient errors in the model will be applied first. The by-treatment-group option is included to the covariance pattern to improve the model efficiency.

If the algorithm for unstructured covariance pattern does not converge, the following covariance structures will be tested in sequence until the model converges: heterogeneous Toeplitz, homogeneous Toeplitz, first-order autoregressive, compound symmetry, and variance component. The sandwich estimator will be used if there is convergence issue. When the random effects model does not converge or does not have a positive definite Hessian, the fixed effects instead of random effects will be performed instead. The Least Square Mean (LSMean) (SE) and 95% CI estimated changes from baseline to Week 52 will be presented.

Sample SAS code:

```
PROC MIXED DATA = XXX;
  CLASS TRTPN SUBJID ItemAgrp;
  MODEL CHG = TRTPN AWK TRTPN*AWK ItemAgrp / RESIDUAL CL COVB DDFM=KR;
  RANDOM AWK / SUBJECT =SUBJID TYPE=UN GROUP= TRTPN;
  LSMEANS TRTPN / at AWK = 52 PDIFF CL;
  ODS OUTPUT LSMEANS=MIXLSMNS DIFFS=MISDIFS;
RUN;
```

(Note: ItemAgrp denotes the categorical Item A (or PUL entry) scores at baseline)

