8.3.4. Efficacy Analyses

The analyses of the efficacy endpoints will be based on subjects in the ITT population.

8.3.4.1. Analysis of Primary Endpoint Change in PUL from Baseline to Week 52

The primary endpoint, Change in the total score of Performance of Upper Limb [(PUL) 2.0 version], from baseline to Week 52 will be analyzed using a random coefficient model with treatment, visit, visit-by-treatment interaction, , and baseline total score of Performance of Upper Limb value as fixed effects; the intercept and linear slope of visit as random effects. The primary analysis will be based on observed data from subjects in the ITT population.

As sensitivity analysis, the analysis of covariance model (ANCOVA) model with Multiple Imputations (ANCOVA –MI) will be also applied. The model will include treatment and baseline total score of Performance of Upper Limb value. The primary analysis will be based on the ITT population.

PUL 2.0 scale:

- The PUL 2.0 scale, total score = 42.
- High Level: Shoulder Dimension, 6 items: Max score = 12
- Mid-level: Elbow Dimension, 9 items: Max score = 17
- Distal level: Wrist and Finger Dimension, 7 items: Max score = 13

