8.3.4.2. Analyses of Secondary Endpoints

Changes in ppFVC and ppPEF from Baseline to Week 52

The Change from baseline to Week 52 in ppFVC will be analyzed using a random coefficient model with treatment, visit, visit-by-treatment interaction, and baseline ppFVC as fixed effects; the intercept and linear slope of visit as random effects. The analysis will be based on observed data from subjects in the ITT population.

The Change from baseline to Week 52 in ppPEF will be analyzed using a random coefficient model with treatment, visit, visit-by-treatment interaction, and baseline ppPEF as fixed effects; the intercept and linear slope of visit as random effects. The analysis will be based on observed data from subjects in the ITT population.

Change in the Grip Strength of the Hands from baseline to Week 52, assessed by Hand Held Myometry (HHM)

The Change from baseline to Week 52 in grip strength of the hands will be analyzed using a random coefficient model with treatment, visit, visit-by-treatment interaction, and baseline value as fixed effects; the intercept and linear slope of visit as random effects. The analysis will be based on observed data from subjects in the ITT population.

Change in Left Ventricular Ejection Fraction percentage (LVEF %) from Baseline to Week 52, Assessed by MRI.

Summary of Listing and the analyses of the change from baseline to week 52 in LVEF (%) assessed by MRI will be conducted in the ITT population.

The change from baseline to Week 52 in left ventricular ejection fraction percentage (LVEF%), as assessed by MRI will be analyzed using a random coefficient model with treatment, visit, visit-by-treatment interaction, and baseline value as fixed effects; the intercept and linear slope of visit as random effects.

As an exploratory endpoint, the dichotomous responder (proportion of patients with change from baseline in LVEF% ≥ 0 at Week 52) will be summarized and analyzed. The logistic regression model will be used to compare the proportion of subjects with change from baseline in LVEF% ≥ 0 . The model will include treatment and baseline LVEF%.

For other secondary endpoints, MMRM model will be used in continuous variables; logistic regression model in binary variables; Cox regression model in time-to-event variables. The analysis models will include appropriate baseline factors. Other methods will be applied as appropriate.

Detailed analyses of all secondary endpoints will be clearly outlined in the SAP.

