#### 6.6.1.1.5. Population Summary for Treatment Comparison

Treatment difference of Least-square mean (LSMean) and SE at week 52 and corresponding 95% CI will be presented.

The random coefficient linear regression model (RCM), where within-patient errors follow a random coefficient regression model will be performed. The RCM model will include fixed effects of time, treatment, treatment-by-time interaction, with baseline ordinal PUL entry score as covariate. The time in the RCM model will be calculated as the elapsed weeks (considered as a continuous variable with 1 decimal place) from first dose date (or randomization date for subjects who drop out prior to any study medication) to the assessment date. All valid values including from unscheduled visits will be included.

The residual plot from the PROC MIXED output will be examined. If the residual plot shows a systematic pattern rather than a random scatter, then the linearity assumption may not be appropriate. In case of non-linearity, MMRM will be used as the primary analysis method, which is currently listed as one of the sensitivity analyses in next section.

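### The SAP's code for the primary random coefficient model has no random intercept although the protocol specifies one, and the last fallback does not say which standard error applies.

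*SAP*

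**What the plan says.** **Protocol.** Section 8.3.4.1 and the Synopsis give the primary RCM "the intercept and linear slope of visit as random effects". Section 8.3.4.2 does the same for ppFVC: "baseline ppFVC as fixed effects; the intercept and linear slope of visit as random effects".

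**SAP text.** Section 6.6.1.1.5 describes a model "where within-patient errors follow a random coefficient regression model will be performed". It lists the fixed effects but does not say which effects are random.

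**SAP code.** The Covariance Structure Strategy gives "RANDOM AWK / SUBJECT =SUBJID TYPE=UN GROUP= TRTPN". PROC MIXED adds no random intercept unless INTERCEPT is written. The code has no REPEATED statement.

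**Covariance sequence.** The text says: "The unstructured covariance structure for the within-patient errors in the model will be applied first". On non-convergence it moves through "heterogeneous Toeplitz, homogeneous Toeplitz, first-order autoregressive, compound symmetry, and variance component". It then says: "The sandwich estimator will be used if there is convergence issue". If the random-effects model does not converge, or its Hessian is not positive definite, "the fixed effects instead of random effects will be performed instead".

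**Reach.** SAP Section 6.6.2.1 refers back to 6.6.1.1.5 for ppFVC and Mid-level PUL, steps 2 and 3 of the testing sequence in Table 1. SAP Section 7 lists several model changes (PUL subscores to RCM, MRI endpoints to ANCOVA, an added MMRM) but no change to the random effects of the primary model.

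**The concern.** A programmer who follows the SAP code and one who follows the protocol would fit different primary models and could report different p-values. The primary test gates the whole fixed sequence, so its standard error should be reproducible from the plan before unblinding.

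All change scores of a subject share one baseline measurement, so some intercept variance is to be expected. Without a random intercept, that variance is split between the residual and the slope, and the Week 52 standard error no longer matches the true sampling variance.

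The covariance sequence does not help. With one random effect, the random-effects covariance in each arm is a single variance, so unstructured and the five alternatives are all the same model. The text applies the sequence to within-patient errors, but the code has no statement that models them. A fit that fails would therefore go straight to the last fallback. SUBJECT=SUBJID appears only on the RANDOM line. Once that line is dropped, nothing links the scores of one subject.

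**Working it through.** **1. The plan's own figures.** With a difference of 2.0, SD 2.9 and a two-sided 0.05 t-test, the noncentral t gives power 0.905 with 46 per arm and 0.870 with 41 per arm. These reproduce 92 subjects for 90% power, and for 82 subjects both the 87% in Section 7 and the at least 85% in Section 3.3. They do not depend on the random-effects specification.

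**2. Inputs.** From the documents: PUL at Weeks 16, 28, 40 and 52 (SAP Table 9), 82 mITT subjects, SD 2.9. Assumed, because the documents give no variance split: 41 per arm, complete data, measurement SD s of 0.5, 1.0 or 1.75 points, intercept SD equal to s, and intercept-slope correlation r. The slope SD b is solved from

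s² + 2·52·r·s·b + 52²·b² + s² = 2.9² = 8.41.

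For s = 1.0 and r = 0: 2704·b² = 8.41 − 2 = 6.41, so b = 0.0487.

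**3. True standard error.** With complete data at common visit times, the slope-only, intercept-and-slope and no-random-effects fits give the same Week 52 estimate, so only the standard error differs. The mean visit week is 34 and the sum of squares is 720, so the leverage at Week 52 is 1/4 + 18²/720 = 0.70. The variance per subject is 8.41 − s² + 0.70·s² = 8.41 − 0.30·s², that is 8.335 / 8.11 / 7.49. The standard error of the difference is √(2·variance/41) = 0.638 / 0.629 / 0.605.

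**4. Standard error as coded.** At the expected REML solution for s = 1.0 and r = 0, the slope-only model puts 1.177 in the residual and 8.072 in the slope term at Week 52. The model variance is 8.072 + 0.70·1.177 = 8.896, so the standard error is √(2·8.896/41) = 0.659. The ratio k to the true standard error is 1.047.

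**5. Type I error** is 2·P(T80 > 1.990·k). For k = 1.047 the threshold is 2.084, which gives 4.0%.

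| r | k, s = 0.5 / 1.0 / 1.75 | Type I error |
|---|---|---|
| +0.3 | 1.027 / 1.073 / 1.170 | 4.4% / 3.6% / 2.2% |
| 0 | 1.012 / 1.047 / 1.149 | 4.7% / 4.0% / 2.5% |
| −0.3 | 0.995 / 1.014 / 1.107 | 5.1% / 4.7% / 3.1% |
| −0.7 | 0.968 / 0.955 / 0.993 | 5.8% / 6.1% / 5.2% |

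The direction reverses at r = −0.21 / −0.41 / −0.68. With zero intercept variance, k is 1.000.

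**6. Power at a difference of 2.0, r = 0.** As coded 86.8% / 86.2% / 84.4%, against 87.3% / 88.1% / 90.5% with a correct standard error: losses of about 0.5, 2 and 6 points.

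**7. Last fallback with independence standard errors.** For s = 1.0 and r = 0 the pooled residual variance is 5.116. The standard error is √(2·0.70·5.116/41) = 0.418, a ratio of 0.418/0.629 = 0.664. Type I error is 2·P(Z > 1.96·0.664), about 19%. In simulation over the 12 combinations in the table (10,000 null trials each) the range was 10.4% to 26.1%. The same fit with a subject-level sandwich standard error gave 4.9% to 5.7%.

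**8. How often the fallback is reached as coded.** The slope-only model was fitted by REML in the same 12 combinations, 100 trials each, with about 15% dropout. None of the 1,200 fits failed to converge or had a non-positive-definite Hessian.

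Item A group and the Kenward-Roger adjustment are left out throughout, and dropout is left out except in step 8. The rates show size and direction; the decimals should not be relied on.

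**The case against.** The code is labelled as a sample, the text keeps the term random coefficient model, and SAP Section 1 presents the SAP as an elaboration of the protocol. On that reading the protocol's random terms still stand. A reader might infer that the sponsor dropped the intercept without declaring it. The documents do not support that: a covariance sequence that makes sense only with two or more random effects points to a slip. The text still does not correct the code, so the two must be reconciled.

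The effect is modest. With s of 0.5 or 1.0 and r = 0, power loss is at most about 2 points. Inflation near 6% needs r around −0.7, which no document suggests. A reader might infer that the missing intercept inflates the primary type I error. In most of the cases above it lowers it.

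A reader might also take 10% to 26% as the trial's expected error rate. It is not. The branch would rarely be reached as coded, and the sentence just before it already names a sandwich estimator. What stands is narrower: that sentence is tied to a convergence issue, does not mention the Hessian trigger or the fixed-effects fit, and does not say that clustering is by subject.

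The MMRM and MI-ANCOVA sensitivity analyses do not use the RANDOM statement, so a material discrepancy could show there. They do not replace the primary p-value.

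**Conclusion.** The inconsistency is clear from the documents: the protocol has intercept and slope, the only SAP definition has slope alone, and Section 7 does not list the change. Following the code gives a miscalibrated primary standard error in general when intercept variance is present. At zero intercept-slope correlation this is slightly to clearly conservative, at the cost in power shown above; the direction is not guaranteed and the effect vanishes without intercept variance. Only the extreme case (s = 1.75) falls below the 85% in SAP Section 3.3 at r = 0. That figure comes from a t-test and is not itself wrong. All sizes rest on assumed variance components.

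The fallback wording is a secondary ambiguity. It becomes more relevant once the intercept is added. In simulation, the by-arm intercept-and-slope fit had a random-effects covariance matrix that was not positive definite in 13% to 70% of trials. That is only a proxy and not the Hessian trigger in the SAP, so the real step-down frequency remains unknown. This should be fixed before database lock.

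**What to change.** 1. For the primary endpoint and the RCM secondary endpoints (ppFVC and Mid-level PUL), write RANDOM INTERCEPT AWK / SUBJECT=SUBJID TYPE=UN GROUP=TRTPN. Name both random terms in the text of Section 6.6.1.1.5.
2. State that if the random-effects model fails, by non-convergence or by a Hessian that is not positive definite, GROUP= is removed first. State that any fit without random effects uses a sandwich standard error clustered by subject, and give its degrees-of-freedom method, because Kenward-Roger adjusts a model-based covariance.

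The cost is a few lines of SAP text and code in an amendment before database lock, with no new data. The downside is that the by-arm intercept-and-slope model has more parameters and may step down more often, so both changes should be made together.

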## 6.6.1.2. Sensitivity Analyses of the Primary Endpoint

### 6.6.1.2.1. MMRM Analysis for Primary Efficacy Endpoint

#### 6.6.1.2.1.1. Estimand Strategy

Same as [Section 6.6.1.1.1](#).

#### 6.6.1.2.1.2. Population of Interest

Same as [Section 6.6.1.1.2](#)

#### 6.6.1.2.1.3. Intercurrent Event Handling Strategy

Same as [Section 6.6.1.1.3](#).

#### 6.6.1.2.1.4. Analysis Variable

Same as [Section 6.6.1.1.4](#).

#### 6.6.1.2.1.5. Population Summary for Treatment Comparison

All post-baseline visits during the double-blind period will be included in the analysis. Change from baseline for the specified endpoints (excluding baseline visits) will be analyzed using a Mixed Model for Repeated Measures (MMRM) approach with fixed effects for treatment, visit (as a factor), treatment-by-visit interaction, and covariates (baseline values). The covariance structure strategy is the same as described in [Section 6.6.1.1.5](#).

Sample SAS code:

```
PROC MIXED DATA = XXX;
  CLASS TRTPN SUBJID AVISITN ItemAgrp;
  MODEL CHG = TRTPN AVISITN TRTPN* AVISITN ItemAgrp / DDFM=KR;
  REPEATED AVISITN / SUBJECT =SUBJID TYPE=UN GROUP= TRTPN;
  LSMEANS TRTPN / at AVISITN = 52 PDIFF CL;
  ODS OUTPUT LSMEANS=MIXLSMNS DIFFS=MISDIFS;
RUN;
```

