### 6.6.2.2.3. Covariance Structure Strategy

The unstructured covariance structure for the within-patient errors in the model will be applied first. The by-treatment-group option may will be added to the covariance pattern to improve the model fit as appropriate.

If the algorithm for unstructured covariance pattern does not converge, the following covariance structures will be tested in sequence until the model converges: heterogeneous Toeplitz, homogeneous Toeplitz, first-order autoregressive, compound symmetry, and variance component, until the model converges. The sandwich estimator will be used if there is convergence issue. If the model doesn't converge for all covariance structures listed above, some least significant factors or interaction terms ( $p > 0.05$ ) can be excluded from the model to achieve convergence. The revised model with fewer factors or interaction terms will be tested using the same sequence as specified above.

Sample SAS code:

*/\* excluding baseline visit \*/*

```
PROC MIXED DATA=MMRM (WHERE=(AVISITN>0));
  CLASS TRTP AVISIT;
  MODEL CHG = TRTP AVISIT TRTP*AVISIT BASE /DDFM=KR;
  REPEATED AVISIT /SUBJECT=SUBJID TYPE=UN GROUP=TRTP;
  LSMEANS TRTP /PDIFF CL;
  LSMEANS TRTP*AVISIT /PDIFF CL;
  ODS OUTPUT LSMEANS=MIXLSMNS DIFFS=MIXDIFS;
RUN;
```

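### The sample MMRM code in SAP 6.6.1.2.1.5 cannot return the Week 52 treatment difference, because it applies AT to a CLASS variable

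*SAP*

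**What the plan says.** SAP 6.6.1 defines the primary endpoint at Week 52, and the null and alternative hypotheses printed there both refer to Week 52. Section 6.6.1.1.5 repeats the target: "Treatment difference of Least-square mean (LSMean) and SE at week 52 and corresponding 95% CI will be presented". The planned model in that section is a random coefficient model (RCM) with time as continuous weeks. If its residual plot shows a systematic pattern, the method changes: "In case of non-linearity, MMRM will be used as the primary analysis method".

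The MMRM is specified in SAP 6.6.1.2.1.5. The prose enters visit as a factor. The sample code agrees and then requests the LS means in a different form:

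- CLASS statement: "CLASS TRTPN SUBJID AVISITN ItemAgrp"
- MODEL statement: "MODEL CHG = TRTPN AVISITN TRTPN* AVISITN ItemAgrp / DDFM=KR"
- LS means: "LSMEANS TRTPN / at AVISITN = 52 PDIFF CL"

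There is no LSMEANS request for the treatment-by-visit term.

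Two other code blocks in the SAP are useful comparators. The RCM code, under the Covariance Structure Strategy heading in 6.6.1.1.5, uses "LSMEANS TRTPN / at AWK = 52 PDIFF CL", and AWK is not on its CLASS statement. The grip-strength MMRM code in 6.6.2.2.3 includes "LSMEANS TRTP*AVISIT /PDIFF CL".

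SAP 6.6.4 sends the primary-endpoint subgroup analyses to the same MMRM when the linear assumption is not met.

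**The concern.** The AT option of LSMEANS evaluates LS means at a chosen value of a continuous covariate. It does not select a level of a classification factor. Every term in this MMRM is built from CLASS variables, so AT has nothing to act on, and nothing else in the block outputs a Week 52 contrast.

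The stakes come from the promotion rule. If linearity is rejected, this model carries the confirmatory test, which heads the fixed testing sequence in SAP Table 1. There are then two possibilities:

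- **The code stops.** Someone must rewrite the contrast at analysis. The residuals being inspected come from a model containing treatment, so this would most likely happen with treatment codes in hand.
- **AT is ignored.** The output is the treatment main effect averaged over all post-baseline visits, which is a different quantity from the Week 52 difference.

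**Working it through.** **1. The plan's own figures.** Inputs from SAP 3.3: difference 2.0, SD 2.9, two-sided alpha 0.05, 90% power, 1:1 allocation.

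- Normal approximation: n per arm = 2 × (1.960 + 1.282)² × 2.9² / 2.0² = 2 × 10.51 × 8.41 / 4 = 44.2, so 45 per arm and N = 90.
- Exact noncentral t: 46 per arm, N = 92, power 90.5%. The stated 92 is reproduced.
- With 82 subjects (41 per arm), the t-test has 87.0% power, which matches the 87% in SAP 7.

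**2. What each LSMEANS request estimates.** The post-baseline PUL visits are Weeks 16, 28, 40 and 52 (SAP 6.6.1.2.3.5 and Appendix 2, Table 9). For a model with treatment, visit and their interaction, the coefficients of the pamrevlumab–placebo difference are:

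| Request | Treatment terms | Interaction terms |
|---|---|---|
| TRTPN alone | −1, +1 | ±0.25 on each of the four visits |
| TRTPN*AVISITN, Week 52 | −1, +1 | −1, +1 on Week 52; 0 on the others |

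The first is the equal-weight mean of the four visit-specific differences. The second is the Week 52 difference.

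**3. Expected value of the averaged contrast when the true Week 52 difference is 2.0.** The documents give no time course for the treatment effect, so each course below is an assumption.

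| Assumed course | Weeks 16, 28, 40, 52 | Average |
|---|---|---|
| Only at Week 52 | 0, 0, 0, 2.00 | 0.50 |
| Quadratic (late) | 0.19, 0.58, 1.18, 2.00 | 0.99 |
| Linear | 0.62, 1.08, 1.54, 2.00 | 1.31 |
| Square root (early) | 1.11, 1.47, 1.75, 2.00 | 1.58 |
| Constant from Week 16 | 2.00, 2.00, 2.00, 2.00 | 2.00 |

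Check of the linear row: mean visit time is (16 + 28 + 40 + 52)/4 = 34 weeks, and 34/52 × 2.0 = 1.31.

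**4. Power of the averaged contrast.** The documents give no SDs or correlations by visit. Assume 82 subjects, complete data, a common correlation ρ between visits, and the linear course.

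- SD 2.9 at every visit: the SD of the four-visit average is 2.9 × √((1 + 3ρ)/4), which is 2.29 at ρ = 0.5 and 2.79 at ρ = 0.9. Power is 72% and 56%.
- SD growing as 2.9 × √(week/52): power is 89% at ρ = 0.5 and 75% at ρ = 0.9.

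The planned Week 52 test has 87%, so the linear range of 56% to 89% lies on both sides of it. With a constant effect, power is 89% or more in every scenario run.

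**The case against.** The strongest reply is that the SAP's text already settles the contrast. The endpoint, both hypotheses and the reporting sentence in 6.6.1.1.5 all say Week 52. The promotion rule changes the method and leaves the endpoint and hypotheses alone. The MMRM section also adopts the covariance strategy of 6.6.1.1.5, and that text closes by promising estimated changes to Week 52. The faulty line itself names 52, the block is labelled sample code with a placeholder dataset, and the grip code shows the working form. All of this stands, and it limits the severity.

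It also rules out several stronger readings that a reader might infer:

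- **That the fallback is planned as a test of the 52-week average.** The text says otherwise. Section 6.6.1.2.1.5 lacks a sentence of its own naming the contrast, but its code is not the only statement of the target.
- **That the confirmatory p-value would be wrong.** This needs non-linearity to be declared, the sample code to be run unchanged, AT to be ignored silently, and the output to pass review without a Week 52 label. SAS was not available, so whether the line stops or is ignored is unknown.
- **That the estimate would be about a third too small, or that power would fall.** The 35% shrinkage holds only for a linear course. Any systematic residual pattern triggers the switch, so a late-emerging effect cannot be presumed. Averaging may also reduce variance enough to offset the smaller difference.
- **That the line was carried over from the RCM code.** The resemblance is plain, but the documents do not show its origin.

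What the reply does not do is make the line work. The code for an analysis that may become primary still cannot deliver its target.

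**Conclusion.** Wrong as written, and minor to moderate in severity. It is certain from the documents that AVISITN is a CLASS factor, that the model has no continuous covariate, and that no treatment-by-visit LS means are requested; given how AT works, the block cannot return the Week 52 difference. The consequence is conditional. Either the code stops and the contrast is rewritten at analysis, or AT is ignored and the result is the four-visit average. In the latter case the expected value for a true 2.0 is 1.31 if the effect grows linearly, and runs from 0.50 to 2.00 over the assumed courses. The direction of any effect on power is not determined. The issue bears on the primary analysis, and on the primary-endpoint subgroup analyses, only if linearity is rejected. The planned MMRM sensitivity analysis is affected in any case.

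**What to change.** In SAP 6.6.1.2.1.5, replace the LSMEANS line with `LSMEANS TRTPN*AVISITN / PDIFF CL;`, the form already used for grip strength in 6.6.2.2.3. Add one sentence to the section stating that the Week 52 pamrevlumab–placebo difference from this statement, with its SE, 95% CI and p-value, is the MMRM result and is the confirmatory test if the MMRM becomes primary. Do not repair the line by taking AVISITN off the CLASS statement: that would make time linear again and contradict the section's own description of visit as a factor.

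The cost is one line of code and one sentence. Nothing changes in the data collected, the sample size or the intended estimand. The correction should be made before unblinding, so that the contrast is not settled with results in view.
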